Our sample size calculation was based using the Roland Morris Disability Questionnaire (RMDQ) score as the primary endpoint. For our primary analysis we use a responder analysis, in which we define clinical significant changes as a 30% reduction in pain disability from baseline, using the RMDQ, and have powered the study to be able to detect this change. This is the accepted threshold for clinically significant improvement in clinical trials and recommended by the IMMPACT guidelines and studies demonstrate that a 30% reduction on the RMDQ is a clinically important difference.^{96,97} Prior studies have shown that 15-20% of usual care patients will demonstrate a 30% reduction in pain function score (using the RMDQ and similar measures) from baseline to follow-up, so in order to detect an absolute difference to 20% in the primary outcome measure between treatment groups (i.e. 15-20% in the usual care group compared with 35-40% in the intervention group), we estimate that we will need between 86-97 people in each group with complete data. This estimate takes into account that we are setting the alpha error rate to look separately at both black and non-black patients. We will use the between-group change on the RMDQ as a secondary measure.

We also need to factor in that up to 50% of the study sample may be non-black, since we want to be able to have power to detect meaningful effects in the subgroup that only includes black patients (~100/50%=200). To allow for up to 20% attrition, we would need to randomize 250 patients for each arm of the study, for a total of 500 patients recruited, and 200 black patients with complete data for the final analyses. We estimate that in order to reach a total of 500 patients randomized, we will need to enroll (i.e. participants who are eligible after the phone screener is completed and are thus mailed a baseline survey packet) as many as 1500 patients. Once we reach the goal of randomizing 500 participants, we will stop enrollment.

Risk vs. Potential Benefit

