5.6. Data Analysis

Phase 1

- **Analysis of focus group data.** Our short timeline for refining the intervention content will require us to identify key insights from our focus groups quickly so that we can use them to guide our revisions on the materials. We will therefore employ rapid assessment process (RAP) methodology to analyze the data collected in this study. RAP is a team-based method that can be used to obtain rich qualitative results in a brief amount of time. A key feature of this method is iterative data collection and analysis where investigators analyze data after each interview. For our study, use of RAP methods will involve scheduling time immediately following each focus group for the investigators participating in data collection ([name] and RAs) to identify and discuss key findings. The list of key findings will be updated and expanded with each subsequent focus group session. Investigator notes from each interview session will be amended to this list of key findings to create a running log of key interview data. The log will be periodically distributed to investigators and discussed during ongoing project meetings.
- **Phase 2 Pilot Data:** There will be no data analysis for Phase 2 Pilot. Although we will be audio-recording the counseling sessions, we plan to use these recordings ONLY to accurately capture the Veteran's reactions to the materials and counseling. We may refer back to the feedback from the Veteran in order to improve our training materials for our counselors, but will not be analyzing the recordings.

Phase 2

- The overall design of the study is a two-arm patient-level randomized trial. All analyses will take this design structure into account and will primarily follow an intent-to-treat analysis where patients are analyzed based on the group they were randomized to regardless of whether or not they actually receive the assigned intervention. Secondary analyses will assess the impact of the intensity of intervention compliance on outcomes and to test study outcomes among patients.
- **Primary Aim.** To test the hypothesis that the intervention will improve chronic pain-specific physical functioning—the primary outcome (H1a), improve emotional functioning, pain intensity and ratings of overall improvement (H1b), and increase walking (H1c), compared to UC for black patients with chronic hip, back, and knee pain.

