- Aims 1a) and 1b)** To compare the effects of the intervention to UC on the IMMEDIATE measures of pain outcomes. The primary measure for these aims is the RMDQ score (i.e. primarily a 30% reduction from baseline and secondarily mean change from baseline), and the other secondary measures are pain intensity, the Profile of Mood States, and the global rating of change scale. Analytic approaches for all of these measures will be similar with the exception that some of the measures are dichotomous (i.e. did the participant have a 30% reduction in RMDQ) while other outcomes are assessed on a continuous scale. For all of these outcomes we will use generalized linear regression fit using appropriate distribution and link functions (i.e. for the primary outcome of whether the patient's RMDQ improved by 30% or more we will fit a binomial distribution and logit links, whereas for the comparison of mean differences between treatment groups we might fit a normal distribution). We expect the RMDQ score to decrease (indicating improvement) in the short term (3-month) as well as over the longer term (6-month) in the intervention group, while improving only slightly from baseline in the control group. For continuous outcomes in this model, for example the RMDQ, scores from both 6 months and baseline will be used as the dependent variable, and the independent variables will include the indicator for the intervention group and an interaction term of 6-month time by intervention group indicator. Each participant will be modeled as a random intercept to allow within-patient correlation of the repeated measures. The model can also include other baseline covariates such as age and pain intensity. The use of a mixed-effects model, rather than using multiple linear regression or analysis of

covariance with change-scores or the 6-month values as the dependent variable, will allow us to use data from participants who may be missing either baseline or the 6-month data while giving an unbiased estimate of the outcome comparisons as long as missing-ness is approximately random. The 3-month effect will be similarly assessed.

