- We will assess the time-averaged effect of the intervention on pain-related functional interference and the outcome trends over time using the outcome measures at all three times (including the baseline) as repeated measures nested within patients and using a mixed-effects model. Prior to fitting the mixed-effects model, we will explore the trends graphically by plotting the cross-sectional means of the outcome measures at each measurement time separately by the two study groups. We will also graph the outcome measures by individual participants to assess the participant specific longitudinal pattern over time. The mixed-effects model will be guided by the results of the graphical analyses. For instance, we expect decreasing trends in the outcome measures over time in the intervention group and no particular trends in the control group. If such a pattern is indicated, linear time and an interaction of linear time by intervention group will be included in the model. In this model, if the time variable is not significant and the interaction is estimated with a significant negative coefficient, it would provide evidence for linearly decreasing outcomes (i.e., improvement in function) in the intervention group over the one follow-up period. If, on the other hand, the graphical analyses suggest that the outcomes in the intervention group decrease at 3 months with no noticeable change between 3 to 6 months, we will model this by including time as dummy categorical variables and interaction terms of intervention group by time dummy categorical variables. An appropriate contrast for the covariate adjusted difference in outcome means at 3 months and 6 months between groups will be constructed to estimate and test for the intervention effect. Using this model, mean changes from baseline can also be estimated and tested for each group. If we find no difference in the intervention effect between 3 and 6 months using this model, we will model the post-intervention time together to obtain a time-averaged intervention effect. The mixed-effects models will also include the baseline values of the outcome measure and other baseline covariates to adjust for potential baseline differences between the groups.

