- **Aim 1c)** To compare the effects of the intervention to UC on increasing walking behavior. Walking will be measured by step counts, which are reported based on readings from the Omron HJ-720 ITC pedometer. The effect of the intervention on step counts will be assessed by comparing average daily step counts (or appropriately transformed scores, if the distribution is shown to be skewed) measured over 7 days. We will use a mixed-effects model with the average daily step counts as reported on the baseline survey, during the last week of the 3 month and 6 month measurement points as the dependent variables, with a similar analytic plan as described for Aim 1a.

- **Secondary Aim 1:** To investigate whether key contributors to racial/ethnic disparities targeted by the intervention (motivation to exercise, pain/exercise efficacy, reduction of pain-related fear) mediate improvement in chronic pain outcomes and increases in walking. The key measures for this aim include the Exercise Regularly Scale, the PSEQ-8, and the FABQ Scale 1. Each of these will be measured at baseline, 3- and 6-month, and each has continuous distribution, and therefore, analytic approaches for each of these measures will be identical to that of Primary Aim 1 with the primary objective of assessing the long-term (6-month) effect of the intervention on these outcomes and secondary objective of exploring outcome trends over time. Indirect effects will be directly tested using the bootstrap approach to obtaining confidence intervals to avoid the often-violated assumption underlying Sobel's (1982) method that the sampling distribution of the indirect effect be normal.¹⁰³
- **Secondary Aim 2:** To explore whether the intervention reduces service utilization and use of opioid analgesics. Using similar analytical methods as described for the Primary Aims, we will use generalized linear models to explore whether service utilization and use of opioid analgesics measures are reduced in the intervention group compared to the UC group.

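### The two-time-point mixed model for continuous outcomes lists no time main effect, so as written it does not estimate the between-arm effect if usual care changes

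*Combined protocol and SAP*

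**What the plan says.** Section 5.6, Aims 1a) and 1b), analyses continuous outcomes such as the RMDQ with the baseline and 6-month scores together as the dependent variable and a random intercept per participant. On the fixed effects it says that "the independent variables will include the indicator for the intervention group and an interaction term of 6-month time by intervention group indicator". Other baseline covariates may be added. The 3-month effect is to be assessed in the same way.

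The same paragraph expects the RMDQ to fall in the intervention group "while improving only slightly from baseline in the control group". It justifies the mixed model as using data from participants with one score missing "while giving an unbiased estimate of the outcome comparisons as long as missing-ness is approximately random".

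The target is comparative throughout. The Primary Aim is effectiveness "compared to UC for black patients with chronic hip, back, and knee pain", and the power section (5.1) states: "We will use the between-group change on the RMDQ as a secondary measure".

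The next paragraph of section 5.6 describes separate models with all three time points. There, in the linear version, "linear time and an interaction of linear time by intervention group will be included in the model"; the categorical version has time dummies and their interactions with group. For the mediator scales (Secondary Aim 1), "analytic approaches for each of these measures will be identical to that of Primary Aim 1".

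**The concern.** A two-time-point model needs a time term so that the usual-care arm can change. Without it, and with 0/1 indicators, usual care has one fitted mean for both visits. The optional baseline covariates do not vary over time and cannot supply the missing term. Any improvement shared by both arms is then credited, wholly or partly, to the intervention. The plan itself expects some improvement in usual care, so the condition that triggers the bias is one the authors anticipate. At stake are the validity of the secondary continuous comparisons and the plan's own claim that they are unbiased.

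**Working it through.** **The plan's figures.** The documents give no figure for this model. The nearby 86-97 per group belongs to the responder endpoint. A pooled two-proportion calculation at two-sided 0.025 and 80% power (both assumed) gives 88 and 99, within 2 of the stated values. The argument below does not depend on it.

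**Inputs.**
- From the documents: the listed model terms; 200 black patients with complete data, hence 100 per arm; 250 randomised per arm with up to half non-black, hence 125 black patients per arm before 20% attrition.
- Assumed: no true treatment effect, equal unit variance at both visits, correlation ρ = 0.6 (range 0.3-0.7), two-sided 5% test.

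**Step 1: fitted means.** Let α be the intercept, β the group term and γ the interaction.

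| Arm | Baseline | 6 months |
|---|---|---|
| Usual care | α | α |
| Intervention | α + β | α + β + γ |

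**Step 2: bias.** Let both arms start at μ, with true changes dC (usual care) and dT (intervention). The true effect is dT − dC. With complete data:
- α = μ + dC/2, the average of the two usual-care means.
- γ = dT, so its error is dC.
- β + γ = dT − dC/2, so its error is dC/2.

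Example in RMDQ points: dC = −1 and dT = −3, so the truth is −2. The interaction gives −3.0 and the 6-month difference gives −2.5. Neither error depends on SD, correlation or sample size.

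If a share m of 6-month scores is missing, the weight of the 6-month mean in α is w = [(1 − m)/(1 + ρ)] / [2(1 − m)/(1 + ρ) + m]. With m = 0.2 and ρ = 0.6, w = 0.5/1.2 = 0.417. The 6-month difference then carries 1 − 0.417 = 0.583 of dC. The interaction still carries all of it.

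**Step 3: standard errors (n = 100 per arm, ρ = 0.6, SD units).**
- Listed interaction: √[2(1 − ρ)/n] = √0.008 = 0.0894.
- Listed group plus interaction: √[1/n + (1 + ρ)/(2n)] = √0.018 = 0.1342.
- Interaction with time added: √[4(1 − ρ)/n] = √0.016 = 0.1265, with bias 0.

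**Step 4: false rejection.** With bias b, the rate is Φ(−1.96 + b/SE) + Φ(−1.96 − b/SE). For a shared shift of 0.1 SD the interaction has b/SE = 0.1/0.0894 = 1.118, which gives 20.1%.

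| Shared improvement (SD) | Listed interaction | Listed 6-month difference | Interaction, time added |
|---|---|---|---|
| 0 | 5.0% | 5.0% | 5.0% |
| 0.05 | 8.6% | 5.4% | 5.0% |
| 0.1 | 20.1% | 6.6% | 5.0% |
| 0.2 | 60.9% | 11.6% | 5.0% |
| 0.3 | 91.8% | 20.1% | 5.0% |

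**Step 5: sensitivity at 0.1, 0.2 and 0.3 SD.**
- Correlation 0.3-0.7 and 86-100 per arm: interaction 12-25%, 35-73% and 65-97%; group difference 6.3-6.8%, 10.5-12.2% and 17.6-21.5%.
- At an assumed 2.5% level (the plan adjusts alpha for two race groups but gives no number): interaction 13%, 50% and 87%; group difference 3.5%, 7% and 13%.
- Simulated REML random-intercept fits, 125 per arm, about 20% of 6-month scores missing (completely at random, or dependent on baseline): interaction about 21%, 61-63% and 92-93%; group difference 7-8%, 15-16% and 28%.
- With the time term added, simulated rejection was 4.8-6.0% in every setting, including complete data.

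**The case against.** The strongest reply is that this is a drafting slip. The text says the variables will include these terms, which need not be a full list. The three-time-point models in the next paragraph pair time with its interaction, and the stated target is always a between-group comparison. That is probably right about intent. But those models serve a separate analysis whose form depends on graphs, and they do not amend this one. An analyst who follows the paragraph literally fits the wrong model.

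Second, the bias depends on coding. If both variables enter as categorical factors, the same two terms imply a usual-care time effect and the bias disappears. With −0.5/+0.5 group coding and equal arms, the interaction is also unbiased. This is correct, but the plan says indicator, which points to 0/1, and this paragraph names no contrast.

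Third, the plan disagrees with itself on the trigger. The three-time-point paragraph expects no trend among controls, and if usual care does not change, both estimates are correct. That stands as a limit on the size, but a valid between-arm analysis should not depend on it.

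Fourth, the error rates rest on assumed inputs, and slight improvement points to the low end: at 0.05 SD the interaction test rejects 8.6% of the time. The 6-month difference, where inflation is mild, is not named for this model. The nearest wording, "An appropriate contrast for the covariate adjusted difference in outcome means at 3 months and 6 months between groups", belongs to the separate models. These points limit how firmly any one percentage can be stated. They do not touch the algebra.

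**Conclusion.** The concern holds: the model as listed is wrong for its stated purpose. With 0/1 indicators, the interaction is off by the whole usual-care change, and the 6-month difference by half of it (about 0.58 with 20% of 6-month scores missing and correlation 0.6). The error favours the intervention if usual care improves and works against it if usual care worsens. The bias fractions follow from the listed terms; the rejection rates are illustrations.

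Affected are the RMDQ mean-change analysis, its 3-month version, the other continuous outcomes with a baseline value, and the intervention-effect models for the mediator scales. Step counts are affected only if this model form is used for them. Not affected are the primary 30% responder logistic analysis, the sample size, and the global impression of change, which has no baseline value. For the bootstrapped indirect effects, the plan does not say which model supplies the intervention-to-mediator path, so the effect there cannot be judged.

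This should be fixed, but it does not threaten the primary result.

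**What to change.** Reword the sentence along these lines: *the independent variables will include an indicator for 6-month time, the intervention-group indicator, and their interaction; the treatment effect is the interaction, that is, the between-arm difference in change from baseline.* Use the same wording for the 3-month model, the other continuous outcomes with a baseline value, and the mediator scales. For step counts, state which model form applies; if it is this one, include indicators for both follow-up times.

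A model with time and time-by-group but a common baseline mean would also be unbiased under randomisation. It is somewhat more precise: √[2(1 − ρ²)/n] = √0.0128 = 0.113 SD at 100 per arm and ρ = 0.6, against 0.126. Either is acceptable if named in advance.

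The cost is one sentence of analysis-plan text, with no change to data collection, the primary analysis or the sample size. The interval becomes wider than the listed interaction would give, but correct: the SE rises from 0.089 to 0.126 SD at ρ = 0.6, or from 0.118 to 0.167 SD at ρ = 0.3.

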Participants who were found eligible and completed the baseline but were not immediately randomized (due to coaching staffing issues, randomization was putting on hold at the end of 2016 and beginning of 2017), will be given an additional call to see if they are still interested in participating. Trained interviewers will use a script to 1) remind the participant of about the study and review the purpose and what is involved; 2) ask if they are still interested in participating; 3) go through the eligibility questions again if they are interested. If they are interested and found eligible, they will be mailed a baseline survey and will receive another \$20 for completion. Upon baseline return, they will be

randomized and be treated the same as all other randomized participants for the duration of the study.

- If eligible, the participant will receive the baseline survey in the mail. Once they return the baseline survey, a chart review will determine if they are eligible, and if so, the subject will be randomly assigned to the Usual Care (UC) or Intervention condition. We will continue to contact patients until we have our required sample of 500 eligible patients (250 to each arm). Intervention participants will be mailed an introductory letter, informational brochure, and Veteran's Workbook (to be used during coaching sessions) shortly before being called to schedule their first counseling session. Patients in the UC condition will receive an informational brochure. Recruitment (via the administration of a brief telephone screening questionnaire), baseline, 3 and 6-month surveys, and telephone coaching will be conducted at the Minneapolis VA. The study coordinator and/or research assistants will attempt to call the participants for a maximum of 3 times at different times of the day at each of the recruitment and data collection timepoints (eligibility, baseline, 3-month, and 6-month).
- **Describe materials that will be used to recruit subjects, e.g., advertisements. Include materials as an appendix or separate attachment.**

See IRB supporting documents

Subject payments:

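### The two-wave model for continuous outcomes is a change-score comparison that gives up precision, and its stated advantage over ANCOVA does not hold

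*Combined protocol and SAP*

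**What the plan says.** Section 5.6, Aims 1a) and 1b), ranks the two RMDQ measures as "primarily a 30% reduction from baseline and secondarily mean change from baseline". For continuous outcomes it takes the baseline and 6-month scores as responses with a random intercept per participant, and "the independent variables will include the indicator for the intervention group and an interaction term of 6-month time by intervention group indicator". It names no time main effect. It adds: "The model can also include other baseline covariates such as age and pain intensity". It sets ANCOVA aside on the ground that the mixed model "will allow us to use data from participants who may be missing either baseline or the 6-month data" and stays unbiased if data are missing at random.

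The next bullet of section 5.6 describes a second mixed model with all three waves as responses. Linear or categorical time is chosen after plotting the outcome by arm. In the categorical branch, a covariate-adjusted difference at 3 and 6 months is tested. The baseline value of the outcome is also entered as a covariate.

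On the order of events, section 5.2 says: "Once they return the baseline survey, a chart review will determine if they are eligible, and if so, the subject will be randomly assigned". Section 5.1 (Study Design) gives the same order. Section 5.1 (Power and sample size) allows for up to 20% attrition.

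**The concern.** With a free group effect and a group-by-time term, the baseline arm means are estimated separately even though randomisation makes them equal in expectation. The treatment effect then becomes a difference in change scores. Baseline adjustment uses the same data and is more precise unless the two waves are perfectly correlated. The optional covariates give an impression of adjustment that this estimate does not receive.

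The outcomes at stake are those with a baseline score that use this model: RMDQ mean change, PEG, the emotional functioning measures and the psychological mediators. Their confidence intervals would be wider than the data require. The plan also leaves open which of its two models supplies the reported 6-month effect.

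**Working it through.** **The plan's own figure.** The only sample-size figure is for the binary endpoint: 86 to 97 completers per group, for "15-20% in the usual care group compared with 35-40% in the intervention group". The text says it is "setting the alpha error rate to look separately at both black and non-black patients" but gives no alpha or power. Assuming two-sided alpha 0.05/2 = 0.025 and 80% power, the arcsine formula n = 2(2.241 + 0.842)²/h², with h = 2·asin√p1 − 2·asin√p2, gives 85.8 (h² = 0.2216) and 97.2 (h² = 0.1955). The figure is reproduced. Then 200/0.8 = 250 per arm. None of this uses the continuous model, and the documents give no SD or correlation for any continuous outcome.

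**What the interaction estimates.** A time main effect is assumed here. Read literally without one, the interaction is the intervention arm's own pre-post change: with no treatment effect and a common change of −0.2 SD, simulation returned −0.20. With a time effect and complete data, one simulated data set gave an interaction of 0.0545 (SE 0.1281), identical to the raw difference in change. ANCOVA on the same data had SE 0.1104, and (0.1104/0.1281)² = 0.74. Adding a time-invariant covariate correlated with the outcome moved the estimate by about 1e-15 and left the SE unchanged.

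**Size of the loss, complete data.** With equal SDs σ at both waves, correlation rho and n per arm, the per-arm variances are:

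- interaction: 2(1−rho)σ²/n
- ANCOVA: (1−rho²)σ²/n

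Their ratio is (1+rho)/2, so the loss is (1−rho)/2.

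**With a share f of 6-month scores observed:**

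- interaction: σ²[(1−rho²)/(fn) + (1−rho)²/n]
- ANCOVA: σ²(1−rho²)/(fn)

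The loss is (1−rho)/[(1+rho)/f + (1−rho)]. At rho 0.5 and f 0.8 this is 0.5/(1.875 + 0.5) = 21%.

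| assumed rho | loss, complete data | loss, 20% missing at 6 months | 200 completers worth, 200(1+rho)/2 |
|---|---|---|---|
| 0.3 | 35% | 30% | 130 |
| 0.4 | 30% | 26% | 140 |
| 0.5 | 25% | 21% | 150 |
| 0.6 | 20% | 17% | 160 |
| 0.7 | 15% | 12% | 170 |
| 0.8 | 10% | 8% | 180 |

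Simulation with 125 per arm agreed: 37%, 24%, 21%, 15% and 10% at rho 0.3, 0.5, 0.6, 0.7 and 0.8 with complete data, and 21% and 16% at rho 0.5 and 0.6 with 20% missing.

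**Does missing 6-month data favour the two-wave model?** A patient with only a baseline score adds nothing about the 6-month effect given baseline. In the two-wave model that score only feeds the arm's free baseline mean. At rho 0.5 with 20% missing, the simulated variances (in units of σ²/n per arm) were 1.156 for the interaction, 1.168 with a covariate added and 0.914 for ANCOVA, with mean estimates within 0.004 of zero under no effect.

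**The second model.** Its adjusted 6-month contrast comes close to ANCOVA:

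- complete data: 0.761 v 0.739 at rho 0.5 (3% loss); 0.685 v 0.660 at rho 0.6 (4%)
- 20% missing: 0.991 v 0.914 at rho 0.5 (8%); 0.856 v 0.809 at rho 0.6 (5%)

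The interaction term in that same model keeps the full loss (0.971 at rho 0.5 with complete data).

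**The case against.** The strongest reply is that the plan already contains the remedy. The second model uses all three waves, offers categorical time, enters the baseline value and tests an adjusted contrast, which recovers most of the loss. That much stands, but it does not settle the matter. The contrast belongs to one branch, chosen after plots by arm; in the linear branch the test is the time-by-group interaction. Using baseline as both response and covariate means the baseline record is regressed on itself, which the random-intercept structure cannot describe. Secondary Aim 1, which says its analysis matches Primary Aim 1, puts the 6-month effect first and trends second. That points to the two-wave model as the main analysis, though the plan never says so.

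A reader might infer that the reason for rejecting ANCOVA can never arise. The documents do not support that. The reason also covers missing 6-month data, which are expected. Baseline gaps within a returned survey are possible too: participants may refuse any question (section 5.1, Risk vs. Potential Benefit), and no completeness rule is given. What fails is the step from such gaps to a preference for this model. A model with constrained baseline means keeps those patients as well.

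It is also fair that mean change is the secondary measure the plan names, and that the interaction, with a time term, estimates it validly. Under randomisation the baseline-adjusted contrast has the same target, so nothing is given up by changing.

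**Conclusion.** The concern holds as a loss of precision in secondary continuous analyses. Relative to baseline adjustment it is 35% down to 10% of the information for rho 0.3 to 0.8 with complete data, and about 30% down to 8% with 20% attrition. These figures assume rho and equal SDs at the two waves. With unequal SDs s0 (baseline) and s1 (6 months) and complete data, the excess per-arm variance is (s0 − rho·s1)²/n. This is never negative but may be smaller or larger. It matters for PEG, where entry requires a screening score of at least 5.

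Stronger conclusions that a reader might draw are not supported:

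- A single loss such as 20–25% requires rho of 0.5 to 0.6 with complete follow-up, which the documents do not state.
- Not every continuous outcome is affected in this way. The global change scale has no baseline (Table 3), and Aim 1c names three waves of step counts.
- A chance baseline difference d does not carry over in full. It shifts the change-score estimate by rho·d − d = −(1−rho)d, for example −0.5d at rho 0.5.
- There is no bias from this source, and the primary responder analysis and its 86 to 97 per group are untouched.

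**What to change.** Replace both continuous models in section 5.6 with one prespecified longitudinal model:

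- baseline, 3-month and 6-month scores as responses
- categorical time main effects
- baseline means constrained equal across arms, that is, no group main effect
- group-by-3-month and group-by-6-month terms
- unstructured covariance
- the 6-month contrast as the reported effect

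Do not also enter the baseline score as a covariate, and do not let plots by arm decide the form of time. Delete the sentence that rejects ANCOVA.

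An acceptable but not fully equivalent alternative is ANCOVA of the 6-month score on arm and baseline score. It drops patients whose only follow-up is at 3 months and needs a rule for missing baseline items. Compare the global change scale between arms at follow-up without a baseline term.

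The cost is wording only: Table 3 already schedules all three waves for these measures. The change should be fixed before any comparison by arm is run.
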